## 1 Introduction

Prostate cancer (PC) is the most common cancer among men. The incidence of PC has increased dramatically in Finland since 1980's and lately approximately 4.500 new PC cases have been diagnosed annually in Finland.

About one quarter of diagnosed PC are metastatic at the time of diagnosis. Accurate staging is extremely important, as the stage is single most important factor when treatment decisions are made and stage is the single most important prognostic factor. Localized PC is treated with active surveillance (low risk cases), or with treatment modalities with curative intent (radical prostatectomy or radiotherapy). Although recently radical treatments have been suggested to play a role in low volume metastatic disease, the standard treatment of metastatic disease is castration therapy.

In PC staging the most important anatomic locations to be imaged are i) bone, ii) lymph nodes (especially pelvic lymph nodes), and iii) extranodal soft tissues.

Detection of tumor bone metastases is commonly performed by bone scintigraphy (BS). However, the results of recent studies have raised many doubts whether BS is as effective for confirming or excluding metastatic bone disease. Moreover, the sensitivity for 99mTc-methylene diphosphonate bone scintigraphy (99mTc-MDP BS) is only 50-70%. The detection of bone metastases in patients with high-risk PC is significantly improved by SPECT compared to planar BS. Other imaging modalities with potentially improved accuracy to detect bone metastases in PC include PET-scan and whole body MRI.

The value of positron emission tomography (PET) imaging depends on the suitability of used isotope tracer to identify lesions of the imaged tumor type. When bone is imaged with PET, F-fluoride has been the most commonly used tracer. Other commonly used PET tracers in PC include F-FDG, and F/C-choline, but both have been late more or less replaced by PSMA-PET. Prostate-specific membrane antigen (PSMA) is a trans-membrane protein with an increased expression on cell membranes of PC cells. Ga-PSMA HBED-CC (Glu-NH-CO-NH-Lys- (Ahx)-[Ga(HBED-CC)]) was designed as an extracellular PSMA inhibitor for PET imaging and has been shown to demonstrate high specificity for PSMA-expressing tumor cell. PSMA-PET results have been reported in several studies, but only in three prospective, one including 20-30 patients. Of those studies only study by Fendler and coworkers investigated overall staging, the other two focused on intraprostatic tumor

detection or nodal metastases (van Leuwen). Nevertheless, the Ga-PSMA is a promising imaging modality both for soft tissues and bone. Recently Ga-PSMA was reported to outperform 99mTc-DPD-SPECT in detection of bone metastases in PC.

Recently, the novel PET tracer F-PSMA-1007 has been developed as a promising PSMA ligand to compete and even outperform Ga-PSMA-PET in overall staging. F-PSMA-1007 have some advantages in comparison to Ga-PSMA-PET including primary elimination of F-PSMA-1007 via the hepatobiliary excretion route leading to less bladder isotope activity. Consequently, F-PSMA-1007 might lead to better local staging because of its favorable pharmacokinetics and tumor-specific uptake. F-PSMA-1007-PET combined with CT or even MRI could truly offer a 1-stop solution for both metastatic screening and local staging, but more prospective studies are needed to confirm this hypothesis.

Whole-body T1-weighted MRI is an effective method for bone imaging and is superior when compared to 99mTc-MDP BS. If combined with soft tissue imaging, bone and nodal imaging may be performed in single imaging session. Diffusion-weighted imaging (DWI) as a part of routine MRI examination is a promising tool for detection of an early intramedullary malignant lesion before cortical destruction or reactive processes due to bone marrow metastasis. DWI performs high contrast resolution between tumor and normal tissue. Individual variability of the mean apparent diffusion coefficient (ADC) values, as the result of DWI, may decrease the diagnostic accuracy of DWI. Diagnostic accuracy of DWI for detection of malignant lesion is better than 18-fluoro-deoxy-glucose (FDG) and for detection of bone metastasis is comparable to C-choline. However, it is unclear if it is superior compared to the standard T1-weighted imaging or STIR fat suppression technique. Currently there is not sufficient data comparing MRI and Ga-PSMA and/or F-PSMA accuracy on bone imaging in PC.

In addition to bone, the possible tumor spread to soft tissues, especially pelvic lymph node is common in PC staging. Traditionally contrast enhanced abdomen and pelvic CT or MRI are used but the sensitivity of these imaging modalities is very limited. Diffusion-weighted MRI may improve the diagnostic accuracy when normal sized lymph nodes are evaluated. Still, different PET-tracers and recently especially Ga-PSMA and novel F-PSMA have both been considered as the most promising modalities for pelvic lymph node metastasis detection in PC and preliminary results suggest superior diagnostic accuracy of PSMA-PET compared to other modalities.

We have previously investigated different imaging modalities for detection of bone metastases in prospective setting (Skeleta-trial). According to that study, F-NaF PET-CT and whole-body MRI are superior when compared to 99mTc-MDP SPECT-CT or 99mTc-MDP planar bone scan. Nevertheless, that study needs validation and further investigations as it was limited by low number (n=27) of PC patients, and PSMA-PET was not included in the study.

## **2 Rationale for the study**

Clinicians face challenges when choosing optimal imaging modality/modalities for individual patient. Guidelines do not support any imaging in low risk cases. For intermediate risk cases, and also for high-risk cases, if local treatment is planned, accurate staging of pelvic lymph node is important. In contrary, in very high-risk cases the knowledge of distant (bone) metastases is the single most important staging data. Optimally for clinicians most appropriate imaging technique would be chosen based on patient related risk factors or a single imaging modality would offer all aspects of needed staging information. The rationale for the present study is to find the most appropriate staging modality in high-risk PC at the time of initial staging.

## **3 Objectives of the study**

The specific aims of the study are as follows:

- i)** To compare the diagnostic accuracy of F-PSMA-1007 to 99mTc-MDP planar bone scintigraphy in pessimistic, patient-based analysis for diagnosis of bone metastases in the initial staging of patients with PC.

Secondary objectives

- i)** To compare the diagnostic accuracy of novel imaging modalities (F-PSMA-1007, whole-body MRI including DWI, 99mTc-HMDP SPECT-CT) to traditional imaging modalities (99mTc-HMDP planar bone scintigraphy, and contrast enhanced CT of the thorax/abdomen/pelvis) for diagnosis of bone metastases in the initial staging of patients with PC.
- ii)** To compare the diagnostic accuracy of novel imaging modalities (F-PSMA-1007 PET/CT, whole-body MRI including DWI, 99mTc-HMDP SPECT-CT) to traditional imaging modalities

(contrast enhanced CT of the thorax/abdomen/pelvis) for diagnosis of soft tissue metastases in the initial staging of patients with PC.

- iii) To compare the effect of staging results of novel imaging modalities ( $^{18}\text{F}$ -PSMA-1007 PET/CT, whole-body MRI including DWI,  $^{99\text{m}}\text{Tc}$ -HMDP SPECT-CT) to staging achieved with traditional imaging modalities ( $^{99\text{m}}\text{Tc}$ -HMDP planar bone scintigraphy, and contrast enhanced CT of the thorax/abdomen/pelvis) in terms of the effect of staging on clinical treatment decision.

## **4 Patient selection**

Following criteria are applied when patients are selected for the current study.

### **4.1 Inclusion criteria**

1. Age > 18 years
2. Histologically confirmed PC without previous PC treatment
3. High-risk PC defined with one or more of the following criteria: Gleason  $\geq 4+3$ , PSA  $\geq 20$ , cT $\geq 3a$
4. Adequate physical status defined (by treating clinician) as capability to undergo some form of active treatment for the PC and the physical status allowing the patient to undergo all study imaging modalities
5. Signed informed consent

### **4.2 Exclusion criteria**

1. Previous PC treatment. Short-term androgen deprivation therapy is permitted if necessary for symptomatic and/or very high-risk PC patients
2. Contraindications for MRI (cardiac pacemaker, intracranial clips etc.)
3. Claustrophobia

## **5 Study design**

This is a non-randomized prospective single-institutional study comparing the diagnostic accuracy of novel imaging modalities ( $^{18}\text{F}$ -PSMA-1007 PET/CT, whole-body MRI including DWI,  $^{99\text{m}}\text{Tc}$ -HMDP SPECT-CT) to traditional imaging modalities ( $^{99\text{m}}\text{Tc}$ -HMDP planar bone scintigraphy, and contrast enhanced CT of the thorax/abdomen/pelvis).

## **6 Study endpoints, statistical considerations, and sample size**

### **6.1 Study endpoints**

The primary endpoint of the study is

1. Comparison of AUC values of  $^{18}\text{F}$ -PSMA-1007 to  $^{99\text{m}}\text{Tc}$ -HMDP in pessimistic, patient-based analysis detecting of bone metastases in the initial staging of high-risk PC patients.

The secondary end-points include

1. The sensitivity, specificity, accuracy and AUC value of  $^{18}\text{F}$ -PSMA-1007, whole-body MRI including DWI,  $^{99\text{m}}\text{Tc}$ -HMDP SPECT-CT,  $^{99\text{m}}\text{Tc}$ -HMDP planar bone scintigraphy and contrast enhanced CT detecting bone metastases in the initial staging of high-risk PC patients.
2. The sensitivity, specificity, accuracy and AUC value of  $^{18}\text{F}$ -PSMA-1007, whole-body MRI including DWI,  $^{99\text{m}}\text{Tc}$ -HMDP SPECT-CT,  $^{99\text{m}}\text{Tc}$ -MDP planar bone scintigraphy and contrast enhanced CT detecting lymph node metastases in the initial staging of high-risk PC patients
3. The sensitivity, specificity, accuracy and AUC value of  $^{18}\text{F}$ -PSMA-1007, whole-body MRI including DWI,  $^{99\text{m}}\text{Tc}$ -HMDP SPECT-CT,  $^{99\text{m}}\text{Tc}$ -HMDP planar bone scintigraphy and contrast enhanced CT detecting soft tissue metastases (excluding pelvic lymph node metastases) in the initial staging of high-risk PC patients
4. The effect of staging on clinical treatment-decisions

As in some cases the definition of a metastatic lesion is not confirmed with absolute certainty (e.g. with histological diagnosis) the final diagnosis concerning the metastatic status will be determined during follow up consisting of appropriate imaging modality and follow-up information from other parameters, especially PSA levels.

## **6.2 *Statistical considerations and sample size***

The power calculations are made according to our primary endpoint and on the basis of previously published work, the SKELETA trial. To be able to detect the 19% difference using a two-tailed test with a power of 80% at a significance level of 0.05 in a 2:1 ratio of sample sizes in negative/positive groups, 48 cases and 24 positive cases are required. Together 72 patients will be the sample size and taking into account possible dropouts, permission for 80 patients will be applied for Ethical Committee.

Equivocal findings of the imaging modalities will be classified either as suggestive for metastases (“pessimistic analysis”) or suggestive for non-metastatic origin (“optimistic analysis”). Sensitivity and specificity values of patient-, region- and lesion-based analyses will be compared using McNemar test and two-sided p-values will be calculated. In region-based analysis, diagnostic accuracy values for the detection of bone metastases (sensitivity, specificity, accuracy and AUC) will be calculated from all ROIs which will be pooled into one group. Moreover, receiver operation characteristic curves (ROC) analysis will be performed using 60 000 bootstraps to account for within-patient correlations. Area under the curve (AUC) values will be calculated using the trapezoid rule and compared using a method described by Hanley and McNeil two-sided p-values will be calculated (28). Bootstrap samples will be constructed by stratifying patients based on overall cancer level (cancer present or not) and drawing patients as the independent units with replacement from these groups (cancer present or not). P-values smaller than 0.05 will be considered statistically significant.

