The bone, nodal and extra nodal findings will be compared on patient-, region- and lesion-level. In the region-based analysis for bone metastasis, the skeleton was divided into five regions: head, thorax and ribs, spine, pelvis and limbs. In the lesion-based analysis, only lesions which were highly suspicious or equivocal on at least one imaging modality were included. In addition, maximum of 5 lesions with the highest agreement between modalities per anatomical location (5 locations as defined in the region-based analysis) were included in the lesion-based analysis.

A detailed data collection sheet is applied prospectively for recording separately each individual imaging study results of equivocal, benign and malignant lesion/s.

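### Ordinary McNemar tests on regions and lesions ignore clustering within patients, so those secondary p-values are likely too small if the modality difference is correlated within a patient

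*Protocol*

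**What the plan says.** Protocol Section 6.2 names one test for three levels of analysis: "Sensitivity and specificity values of patient-, region- and lesion-based analyses will be compared using McNemar test". For it, "two-sided p-values will be calculated", and the criterion for every comparison is "P-values smaller than 0.05 will be considered statistically significant". In the region-based analysis, the regions of all patients are pooled.

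Section 7.8 fixes the units. For bone, "the skeleton was divided into five regions: head, thorax and ribs, spine, pelvis and limbs". The lesion-based analysis admits at most five lesions in each of those five locations, so up to 5 × 5 = 25 per patient.

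Section 6.2 also recognises the dependence: the ROC analysis "will be performed using 60 000 bootstraps to account for within-patient correlations", with the patient as the unit that is resampled. That provision is attached to the ROC analysis. Nothing comparable is stated for the sensitivity and specificity comparisons.

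The primary endpoint in Section 6.1 is a patient-based AUC comparison, not a McNemar test.

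**The concern.** McNemar's variance counts every discordant pair as independent information. That holds with one pair per patient. It need not hold when a patient contributes five regions or many lesions, all read from the same scan on each modality. Low tracer uptake or a poor scan on one modality can move all of a man's lesions in the same direction on that modality alone. A few patients with many lesions can then drive the result.

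The paragraph is also inconsistent with itself. It allows for within-patient correlation in the ROC analysis, yet sensitivity and specificity computed from the same clustered units get a test that assumes there is none. At stake is whether region- and lesion-level differences reported as significant at 0.05 carry that error rate. The protocol names the test for these levels, so this is a stated choice and not a detail left to a later analysis plan.

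**Working it through.** **The plan's own figure.** The only related calculation is the sample size: "To be able to detect the 19% difference" "using a two-tailed test with a power of 80% at a significance level of 0.05", "48 cases and 24 positive cases are required", 72 in total. It cannot be reproduced from the protocol alone, because the two AUCs and their correlation are not given. With the Hanley-McNeil variance, 24 positive and 48 negative patients give about 80% power under some assumed inputs: AUC 0.72 vs 0.91 with correlation 0.3 (79-80%), 0.75 vs 0.94 with 0.2 (80-81%), 0.78 vs 0.97 with 0 (79-81%). The figure is not shown to be wrong, and nothing below depends on it beyond the patient counts.

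**Inputs from the protocol.** 24 positive and 48 negative patients; two-sided 0.05; 5 regions; at most 25 lesions per patient.

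**Assumed inputs.** The within-patient correlation, the number of units per patient, and the true sensitivity or specificity.

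**Step 1, formula.** Let d be the difference between modalities on one unit (+1, 0 or -1), m the units per patient and ρ the within-patient correlation of d. The true variance of the summed differences is 1 + (m-1)ρ times the one McNemar uses, so

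true size = 2 × [1 - Φ(1.96 / √(1 + (m-1)ρ))].

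Example: m = 5, ρ = 0.1 gives 1 + 4 × 0.1 = 1.4, then 1.96/√1.4 = 1.66 and a true size of 0.098.

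| Units per patient | ρ = 0 | 0.05 | 0.1 | 0.2 | 0.3 |
|---|---|---|---|---|---|
| 5 | 0.050 | 0.074 | 0.098 | 0.144 | 0.186 |
| 10 | 0.050 | 0.104 | 0.155 | 0.241 | 0.308 |
| 25 | 0.050 | 0.186 | 0.288 | 0.416 | 0.494 |

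**Step 2, simulation of sensitivity with no true difference.** 24 metastatic patients, sensitivity about 0.75, units per patient uniform from 1 to the stated maximum, patient-effect SD 0.5-1.5 on the logit. What matters is how much of the patient variance both modalities share, since a shared effect cancels in d. Type I error of asymptotic McNemar at nominal 5%:

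| Patient variance shared | 1-5 units | 1-10 units | 1-25 units |
|---|---|---|---|
| 0% | 7-14% | 8-23% | 13-39% |
| 50% | 6-9% | 5-16% | 10-30% |
| 80% | 5-8% | 6-10% | 7-19% |
| 100% | 4-6% | 4-6% | 4-6% |

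A patient-clustered test, z = ΣDᵢ / √(ΣDᵢ²) with Dᵢ the sum of d over patient i, stayed at about 4-6%.

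**Step 3, specificity.** With 48 negative patients, 5 regions each and specificity 0.9, asymptotic McNemar gave 0.075, 0.10 and 0.17 at ρ of about 0.06, 0.13 and 0.28. At ρ near 0 it gave 0.050. The clustered test gave 0.044-0.051.

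**The case against.** The strongest reply is that ordinary clustering does no harm here. Only clustering of the *difference* between modalities matters; lesions that are small or faint on both scans cancel out. This is correct, and the last row of the Step 2 table shows it. A reader might infer that the region- and lesion-level p-values are necessarily too small. The documents do not support that, because they give no correlation. Some modality-specific component is plausible, since one tracer targets PSMA expression and the other is a bone agent, but its size is unknown.

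The unit counts are also assumptions. Twenty-five lesions is a cap; a uniform 1-25 implies an average of 13 per metastatic patient, which the protocol does not state. For sensitivity only the metastatic regions count, often fewer than five. An exact McNemar test, which Section 6.2 does not exclude, is conservative with few pairs: 3-6% for 1-5 units with half the variance shared. That can hide weak inflation at region level. It does not rescue the lesion level: with 10 lesions per patient and ρ of about 0.17, the exact test still gave 0.20.

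A reader might also infer that the Hanley-McNeil p-values for pooled-region AUCs rest on independence. That is not established. The Hanley-McNeil sentence stands between two sentences about the bootstrap, and the text is ambiguous about which of them supplies the p-value. It needs clarifying; it is not a demonstrated error.

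Nor do the documents support reading this as a threat to the main result, or treating region and lesion results as the ones most likely to guide practice. The primary analysis is patient-based, and the rationale in Section 2 concerns staging the patient.

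**Conclusion.** The concern holds in conditional form. As written, Section 6.2 applies a test for independent pairs to clustered units, and the p-values are likely too small whenever the modality difference is correlated within patients. With 0-80% of patient variance shared and the other assumptions of Step 2, the true size of the nominal 5% test runs from no material inflation (about 5%) to 14% with 1-5 units per patient, 23% with 1-10 and 39% with 1-25. With all of it shared there is no inflation. These are illustrations over assumed values, not estimates for this trial.

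The effect is confined to secondary region- and lesion-level p-values. The primary patient-based AUC comparison, patient-level McNemar tests, all point estimates and the sample size stand. This should be fixed, but it does not undermine the trial's main conclusion.

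**What to change.** In Section 6.2:

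- Restrict the ordinary McNemar test to patient-level comparisons.
- For region- and lesion-level differences in sensitivity and specificity, take confidence intervals and p-values from the bootstrap already planned, resampling whole patients, or from a McNemar test adjusted for clustering by patient.
- State that p-values for pooled-region AUC comparisons come from the patient bootstrap and not from the unadjusted Hanley-McNeil formula.

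The cost is a few sentences and a small extension of bootstrap code that is needed anyway; no further data or patients are required. The downside is that region- and lesion-level p-values become less favourable where the correlation is present. Because the clustered test kept close to 5% in every scenario examined, including those without correlation, the change is safe whichever assumption proves true.

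### Section 6.2 applies p<0.05 to every secondary comparison of modalities, although only the single primary contrast is prespecified and powered

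*Protocol*

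**What the plan says.** Protocol sections 3 and 6.1 name one primary comparison: the AUC of PSMA-PET against planar scintigraphy for bone metastases, per patient, with equivocal findings counted as metastatic. Section 6.2 sizes the trial for that endpoint alone. The target is a gap of 19%; the design assumptions read "using a two-tailed test with a power of 80% at a significance level of 0.05 in a 2:1 ratio of sample sizes" between the two patient groups, and the result is that "48 cases and 24 positive cases are required".

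The secondary objectives in section 3 each begin "To compare the diagnostic accuracy of novel imaging modalities" or set out a similar comparison. For bone, three novel modalities are set against two traditional ones; for soft tissue, the same three are set against CT. Section 6.1 separates lymph node disease from other soft-tissue disease. Section 7.8 has bone, nodal and extranodal findings compared at three levels.

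For the tests, section 6.2 says "Sensitivity and specificity values of patient-, region- and lesion-based analyses will be compared using McNemar test and two-sided p-values will be calculated". It adds two-sided p-values for AUC differences and defines a pessimistic and an optimistic reading. One rule then covers all of them: "P-values smaller than 0.05 will be considered statistically significant". Nothing in the protocol orders the secondary tests, adjusts them, or calls them exploratory or descriptive.

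**The concern.** The protocol states a decision rule, and the rule is broader than the design supports. Section 2 gives the purpose: "The rationale for the present study is to find the most appropriate staging modality in high-risk PC at the time of initial staging". The primary test answers only whether PSMA-PET differs from planar scintigraphy for bone. Whether MRI or SPECT-CT improves on the traditional modalities, how any of them compares with CT, and what holds for nodes and soft tissue can be learned only from secondary comparisons. As written, each of those may be reported as statistically significant at a nominal 0.05, on numbers chosen for a different question. A reader of the results could not tell a protected finding from one picked out of many.

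**Working it through.** **1. The plan's own figure.** 24 positive + 48 negative = 72, and 72/(1 - 0.10) = 80, so the allowance for dropouts is 10% (implied, not stated). The two AUCs and their correlation r are not given, so 72 cannot be reproduced uniquely. It is attainable: with the Hanley-McNeil variance, a difference of 0.19, two-sided 0.05 and 80% power, 24 positives result for AUCs 0.72 and 0.91 with r = 0.3, for 0.75 and 0.94 with r = 0.2, or for 0.78 and 0.97 with r = 0. The calculation covers one contrast at 0.05 and nothing else.

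**2. The smallest relevant families.**
- Bone pairs: 3 novel x 2 traditional = 6. Less the primary pair, 5 AUC contrasts remain (patient level, pessimistic).
- With sensitivity, specificity and AUC for each pair at that level and reading: 6 x 3 = 18 tests, including the primary.

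**3. Formula.** For m independent tests the chance of at least one false positive is 1 - 0.95^m; for m = 5 this is 0.226. The tests share patients, so a common correlation ρ between test statistics is more realistic. With c = 1.96:

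FWER = 1 - ∫ φ(z) [Φ((c - √ρ z)/√(1-ρ)) - Φ((-c - √ρ z)/√(1-ρ))]^m dz

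| m | ρ = 0.2 | ρ = 0.5 | ρ = 0.8 |
|---|---|---|---|
| 5 | 0.218 | 0.183 | 0.127 |
| 18 | 0.555 | 0.398 | 0.216 |

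The formula gives every test a true size of 0.05. Exact McNemar tests on 24 and 48 patients are conservative: simulated size is 0.010-0.017 for sensitivity and 0.019-0.027 for specificity. The m = 18 row at low and middle ρ is therefore too high, and simulated data are the better guide.

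**4. Simulation.** Inputs: 24 positive and 48 negative patients (section 6.2); five equally accurate modalities; sensitivity 0.70-0.80, specificity 0.80-0.85 and latent correlation between modalities 0.3-0.7 (all assumed, as the protocol gives none); exact McNemar tests; paired AUC test.

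| Family | Chance of at least one p<0.05 |
|---|---|
| Primary AUC test alone | about 0.05-0.06 |
| 5 secondary bone AUC contrasts | 0.20-0.23 |
| 18 patient-level pessimistic bone tests | 0.28-0.34 |
| Patient-level bone tests, both readings | 0.44-0.48 |
| The 5 AUC contrasts under Holm | 0.04-0.06 |

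**5. If some modalities truly differ.** With only the SPECT-CT pairs null, the two bone AUC tests for SPECT-CT give about 0.10. If all sites and both readings are counted at patient level (sites simulated independently, sensitivity 0.75-0.85, specificity 0.80-0.95 assumed), the figure is 0.35-0.39 with only the SPECT-CT pairs null, 0.55-0.62 with the MRI and SPECT-CT pairs null, and 0.68-0.74 with every pair null.

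**The case against.** The strongest reply is that ordering or labelling secondary tests is usually left to the statistical analysis plan, which is not shown, and that 0.05 is merely the conventional threshold. This stands only in part. A missing multiplicity section would be no finding, but here the protocol states an unrestricted rule directly after calling for the p-values, and an analysis plan would have to override it.

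Three stronger readings are tempting, and the documents do not support them.

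- *There is no hierarchy at all.* There is one. The primary is fixed by tracer pair, measure, reading, level and site, and its error rate is intact. What is missing is any control or label within the secondary set.
- *A false claim is likely.* For the bone families in the working, the simulated chance stays below one half, and it assumes equal accuracy throughout. The protocol's own introduction expects SPECT and MRI to improve on planar scintigraphy. Figures above one half need more sites and several true nulls.
- *Some 216 tests are planned.* That product (6 x 3 x 3 x 2 = 108 for bone, plus 2 x 54 for nodes and other soft tissue) is a reader's construction. No lesion-level AUC is specified. With a dichotomised reading the AUC is (sensitivity + specificity)/2, so three measures carry two pieces of information. Readings and levels are alternative views of the same contrast. The formula rates for 108 or 216 tests should not be cited.

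It is also fair that section 2 states a rationale and not a decision rule: nothing says a modality will be preferred because a secondary p-value crosses 0.05.

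**Conclusion.** The point holds for the secondary comparisons only. The primary inference is sound in this respect. The blanket rule lets each secondary comparison be called significant without control, and the excess is material even in the smallest family: about 0.20-0.23 in simulation for five bone AUC contrasts (0.13 by formula at the highest correlation assumed), and about 0.3 for the 18 patient-level pessimistic bone tests, against a nominal 0.05. These figures rest on equal accuracy across modalities and on assumed sensitivity, specificity and correlation. They fall to about 0.10 for the AUC tests of the two SPECT-CT bone pairs alone, and rise as other sites, levels and readings are counted. This should be corrected, but it does not threaten the main result.

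**What to change.** In section 6.2, restrict the p<0.05 sentence to the primary contrast. Add that all other comparisons (sensitivity and specificity, other modality pairs, region- and lesion-based analyses, the optimistic reading, nodal and other soft-tissue disease, treatment decisions) are exploratory and will be reported as estimates with 95% confidence intervals, without claims of statistical significance.

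That label is sufficient. If the sponsor wants confirmatory secondary claims, an option is to test the five remaining patient-based, pessimistic bone AUC contrasts by Holm's procedure at a family-wise two-sided 0.05, and only after a significant primary test. The smallest of the five p-values must then be below 0.05/5 = 0.01.

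The cost is one or two sentences, with no extra patients, scans or reads; sample size and primary power are unchanged. The downside is that secondary contrasts can no longer be called significant at a nominal 0.05.
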